Antidepressant medications are considered first-line treatment for depression. However, studies have found that one-third to one-half of patients do not respond to multiple antidepressants^[11]. A response typically requires at least 4 weeks, and side effects such as nausea, cardiovascular issues, sexual dysfunction, and headaches are common, leading to low medication adherence^[12]. Cognitive Behavioral Therapy (CBT) is a major psychotherapy, but its complexity and cost hinder accessibility for low-income patients with depression^[13]. Thus, despite urgent need, current treatments for major depression remain far from satisfactory.

Vagus Nerve Stimulation (VNS) is an FDA-approved somatic therapy for treatment-resistant depression (TRD) that produces clinically significant antidepressant effects^[14]. However, despite its efficacy, surgical risks, high procedural costs (\$30,000 - \$50,000), and potential side effects limit its appeal and result in low clinical utilization^[15]. To overcome these barriers associated with invasive VNS (iVNS), a non-invasive transcutaneous auricular VNS (taVNS) method has been developed and is garnering increasing attention. Anatomical studies indicate that the ear is the only location on the human body surface with afferent vagus nerve distribution^[16]. According to the "bottom-up" mechanism of the central nervous system, electrical stimulation propagation may follow a reverse pathway from peripheral nerves to the brainstem and central structures^[17]. Therefore, direct stimulation of afferent nerve fibers on the ear should produce effects similar to classical VNS in alleviating depressive symptoms, without the burden of surgical intervention^[18]. The first study on taVNS for depression was conducted in 2009. Since then, a series of clinical studies have demonstrated that taVNS can effectively improve depressive symptoms^[19-21]. However, research on taVNS for treating depression in ACS patients after PCI is limited. We will employ a randomized controlled clinical trial to investigate the antidepressant effect of taVNS in post-PCI patients with moderate or severe depression.

2. Objectives

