2.2 Study Endpoints (or Evaluation Metrics)

2.2.1 Primary Endpoint (or Primary Evaluation Metric) and Definition

Hamilton Depression Rating Scale (HAMD) score at Week 8: The 17-item HAMD is convenient, has clear criteria, is easy to master, and can be used to assess depressive symptoms in various conditions including depression, bipolar disorder, and neurosis, being particularly suitable for major depressive disorder.

Scoring criteria:

No depressive symptoms: Total score ≤ 7 ; Mild depression: Total score ≥ 8 and ≤ 17 ; Moderate depression: Total score > 17 and ≤ 24 ; Severe depression: Total score > 24 .

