2.2.2 Secondary Endpoints (or Secondary Evaluation Metrics) and Definitions

1. Hamilton Anxiety Rating Scale (HAMA) score during follow-up: The total score effectively reflects the severity of anxiety symptoms and can be used to evaluate the severity of anxiety in patients with anxiety and depressive disorders and to assess the effects of various drug and psychological interventions.

According to data from the Chinese Scale Collaboration Group: Total score ≥ 29 : Possible severe anxiety; Total score ≥ 21 : Definite significant anxiety; Total score ≥ 14 : Definite anxiety; Total score > 7 : Possible anxiety; Total score ≤ 7 : No anxiety symptoms.

2. HAMD response rate: Reduction in HAMD-17 score $\geq 50\%$.

3. HAMD remission rate: Post-treatment HAMD-17 score ≤ 7 .

4. Beck Depression Inventory (BDI) score: A tool specifically designed to assess depression severity. The entire questionnaire comprises 21 groups of items, each with 4 statements preceded by corresponding numbers as grade scores.

Scoring criteria: 0-4: (Essentially) no depressive symptoms; 5-7: Mild depression; 8-15: Moderate depression; ≥ 16 : Severe depression.

5. Generalized Anxiety Disorder 7-item (GAD-7) score: The GAD-7 consists of 7 items aiming to understand how often the respondent has been bothered by 7 problems including feeling nervous or anxious over the past 2 weeks.

Scoring rules: Each item scores 0-3, total score 21. 0-4: No generalized anxiety; 5-9: Mild generalized anxiety; 10-14: Moderate generalized anxiety; 15-21: Severe generalized anxiety

6. PTSD Checklist-Civilian Version (PCL-C) score: Developed in 1994 by the Behavioral Science Division of the US National Center for PTSD, translated into Chinese by Professors Jiang Chao and Zhang Jie in 2003. The scale includes 17 items categorized into 3 characteristic symptom clusters: re-experiencing (5 items), avoidance (7 items), and hyperarousal (5 items). Each item uses a Likert 5-point scale from 1 (not at all) to 5 (extremely). Total score range 17-85, with higher scores indicating a higher likelihood of PTSD.

Test results: 17-37: No significant PTSD symptoms; 38-49: Some degree of PTSD symptoms; 50-85: Significant PTSD symptoms, possible PTSD diagnosis

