4.1 Inclusion Criteria

- Age ≥ 18 years;
- Meets diagnostic criteria for ACS;

- 14 days to 12 months post-successful PCI, with stable vital signs;
- Meets Diagnostic and Statistical Manual of Mental Disorders, Fifth Edition (DSM-V) diagnostic criteria for Major Depressive Disorder;
- HAMD-17 score ≥ 7 and < 24 , with HAMA score $<$ HAMD score;
- After full disclosure of condition, the patient or legal representative refuses psychiatric consultation and declines antidepressant medication or psychotherapy;
- Patient or legal representative voluntarily participates in the study and provides written informed consent.

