6.1 Study Intervention Implementation Steps

1. For outpatients or inpatients who are 2 weeks to 12 months post-ACS PCI, a psychiatrist will conduct assessments using DSM-V, HAMD, and HAMA scales. Patients meeting criteria for mild to moderate depression will be advised to receive appropriate treatment. If they refuse and meet inclusion/exclusion criteria, they will sign informed consent, enroll in the clinical trial, and baseline data will be collected.

2. Device Usage Method

Eligible patients will receive transcutaneous auricular non-invasive vagus nerve stimulation while awake. The electrode and the patient's left ear target area will first be disinfected with 75% alcohol. An abrasive gel will then be applied to the left concha cymba and tragus area for gentle abrasion, wiped off, and the area disinfected again with alcohol. Conductive gel will be applied to the electrode output points. The electrode will be placed on the patient's left ear, ensuring the output points are positioned on the left tragus. Pulses will be delivered via the Xidian Keyue brand (Product No.: BS-TVNS600) vagus nerve stimulator. The stimulation current will be gradually increased to the maximum intensity tolerable by the patient, defined as the threshold intensity.

Active Stimulation Group: Stimulation at threshold intensity, with parameters: pulse frequency 20 Hz, pulse width 250 μ s, pulse current 0.5-3 mA. Stimulation cycle: 30 seconds ON, 30 seconds OFF.

Sham Stimulation Group: Device, parameter adjustment, and placement identical to the active group. The stimulator is programmed to deliver stimulation only for the first 5 seconds of each session, with no subsequent stimulation.

Both groups will undergo electrical stimulation twice daily for 20 minutes each session, for a total treatment duration of 8 weeks.

All patients will be trained on how to turn the stimulator on/off, attach the electrode to the ear and position it, and increase the intensity. All subsequent operations will be performed by the patient at home. Patients can obtain assistance via telephone

or site visits if they have questions. Each patient will be given a diary card to record usage date, duration, adverse reactions, and suggestions. Patients are required to complete daily entries, which will be checked during assessment visits.

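### The HAMD-17 entry range overlaps the protocol's own no-symptom and remission cut-off at a score of 7, and its upper limit fits neither the moderate band nor the population named in the introduction

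*Protocol*

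**What the plan says.** Five places in the protocol bear on this.

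- **4.1 Inclusion Criteria** sets the entry range: "HAMD-17 score ≥ 7 and < 24". The same list requires a DSM-V diagnosis of Major Depressive Disorder and a HAMA score below the HAMD score.
- **2.2.1 Primary Endpoint** defines the bands: "No depressive symptoms: Total score ≤ 7 ; Mild depression: Total score ≥ 8 and ≤ 17", then "Moderate depression: Total score > 17 and ≤ 24 ; Severe depression: Total score > 24".
- **2.2.2 Secondary Endpoints, item 3** defines remission: "HAMD remission rate: Post-treatment HAMD-17 score ≤ 7". It sets no condition on the baseline score.
- **1. Introduction**, last sentence, says the trial will "investigate the antidepressant effect of taVNS in post-PCI patients with moderate or severe depression".
- **6.1 Study Intervention Implementation Steps** describes the screened patients differently: "Patients meeting criteria for mild to moderate depression will be advised to receive appropriate treatment". Those who refuse that treatment and meet the eligibility criteria are enrolled.

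**The concern.** HAMD-17 is the entry criterion, the primary endpoint (score at Week 8) and the basis of the response and remission endpoints. Its cut-offs should therefore fit together.

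At the lower end they do not. A score of 7 qualifies for entry and also satisfies the remission threshold if it is still 7 after treatment. Such a patient becomes a remitter without improving, and has at most 7 points to lose on the primary scale.

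At the upper end, the entry limit cuts off the top score of the protocol's moderate band, and the introduction names a severe group that cannot be enrolled. What is at stake is the meaning of the remission rate and the population to which the conclusions apply.

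**Working it through.** The protocol states no figure to reproduce here. The check sets each whole-number score against the protocol's own rules.

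| HAMD-17 at entry | Eligible under 4.1? | Band in 2.2.1 | Fits mild to moderate (6.1)? | Fits moderate or severe (Introduction)? |
|---|---|---|---|---|
| 7 | yes | no symptoms | no | no |
| 8–17 | yes | mild | yes | no |
| 18–23 | yes | moderate | yes | yes |
| 24 | no | moderate | yes | yes |
| 25 and above | no | severe | no | yes |

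**Count of admissible scores.** 23 − 7 + 1 = 17. No-symptom band: 1 (score 7). Mild: 17 − 8 + 1 = 10. Moderate: 23 − 18 + 1 = 6. Severe: 0. Check: 1 + 10 + 6 = 17. Only 6 of the 17 fit the introduction's description; the other 11 do not. These are counts of score values, not of patients.

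**A patient who enters at 7 and stays at 7.** The reduction is (7 − 7)/7 = 0%, so the patient is a non-responder under 2.2.2 item 2 (a reduction of at least 50%) and a remitter under item 3.

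**Effect on the comparisons.** Suppose a fraction p of each arm enters at 7 and stays there whatever the treatment.

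- Remission: if the other patients remit at rates r_A and r_B, the arm rates are p + (1 − p)r_A and p + (1 − p)r_B. The difference is (1 − p)(r_A − r_B).
- Mean HAMD at Week 8: if the difference among the other patients is Δ, the overall difference is (1 − p)Δ.

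Both shrink by the factor 1 − p, and neither changes sign. The protocol gives no value of p. As assumptions only, with the planned 60 per arm:

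| Patients per arm entering at 7 (assumed) | p | Shrinkage of either difference |
|---|---|---|
| 0 | 0 | none |
| 1 | 1/60 = 1.7% | 1.7% |
| 3 | 3/60 = 5% | 5% |
| 6 | 6/60 = 10% | 10% |

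The shrinkage is smaller if some of these patients respond to active treatment. The remission count is affected less if some of them rise above 7.

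**The case against.** The strongest reply is that the overlap is one score value and that 4.1 does not rest on HAMD alone. A patient scoring 7 must also have DSM-V Major Depressive Disorder, assessed by a psychiatrist under 6.1, and a HAMA of 6 or less. If 6.1 is read with the bands in 2.2.1, a score of 7 falls below mild and would not follow the enrolment route at all. Few such patients may enter. All of this stands, and it limits the size of the problem. It does not remove it: 4.1 is the eligibility rule and admits 7, and remission is defined by the HAMD score alone, whatever the diagnosis.

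Four stronger readings are tempting, and the protocol does not support them.

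- **That the trial enrols people who are not depressed.** This is true only of the HAMD band; the diagnosis is required as well.
- **That a patient at 7 is already in remission at entry.** Section 2.2.2 defines remission as "Post-treatment HAMD-17 score ≤ 7". The patient can be counted later without change, but has not met the endpoint before treatment.
- **That the remission or primary comparison is biased.** Randomisation spreads these patients over both arms in expectation, so the effect is dilution. Remission is secondary, and the primary endpoint uses no remission threshold.
- **That the trial cannot meet its aims because severe patients are excluded.** The aims in 2.1 do not mention severe depression, and 4.1 and 6.1 agree in leaving it out. The conflict is with one sentence of the introduction.

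**Conclusion.** The inconsistency is real and narrow. At the lower end, one admissible score lies in the band headed "No depressive symptoms: Total score ≤ 7" and at the remission cut-off, so an unchanged patient at 7 is counted as a remitter. The remission comparison, and to a small extent the HAMD difference, is diluted in proportion to the share of such patients. That share is unknown and may be close to zero; the shrinkage figures rest on assumed shares and on no change in these patients. Neither arm is favoured.

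At the upper end, 24 is moderate by the protocol's own band and yet ineligible, and the introduction and 6.1 describe different populations. As written, the trial can speak only to admitted scores of 7 to 23 in patients with the diagnosis, and not to severe depression.

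This should be fixed because the correction is cheap and the remission rule misfires when followed as written. It does not threaten the validity of the primary comparison.

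**What to change.** Reconcile the introduction and sections 2.2.1, 2.2.2, 4.1 and 6.1 on three points.

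1. **Lower limit and remission.** Either the entry range should not overlap the protocol's own no-symptom and remission cut-off, or remission should be counted only in patients above that cut-off at baseline. The second option leaves eligibility untouched. It still compares randomised groups, because the subset is fixed before treatment.
2. **Upper limit and moderate band.** The two should agree on a score of 24. Which of them changes is a clinical decision for the investigators. Changing the entry limit would alter who is enrolled; changing the band would not.
3. **Population named.** The introduction, 6.1 and the eventual conclusions should describe the patients actually enrolled, with no claim about severe depression.

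The cost is a wording amendment. Depending on the choice under point 1, the trial may lose the few patients who score exactly 7, or drop them from the remission comparison only. If point 2 is settled by moving the entry limit, patients scoring 24 would be added, and the amendment should say so.

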4.2 Exclusion Criteria

- Severe heart failure (NYHA class \geq III);
- Uncontrolled hypertension ($\geq 180/110$ mmHg);
- First-degree atrioventricular block on awake ECG (PR interval ≥ 0.20 s), or occurrence of Mobitz type II second-degree or third-degree AV block at any time;
- 24-hour average heart rate ≤ 50 beats per minute, RR interval ≥ 3 s, or history of syncope unrelated to the current ACS;
- Patients on dialysis;
- History of renal denervation or vagal ganglion ablation therapy;
- Life expectancy less than 4 months;
- Pre-existing clinical diagnosis of other severe psychiatric disorders prior to PCI, including schizophrenia, severe intellectual disability, substance abuse;
- Patient currently taking antipsychotic medications;
- High suicide risk;
- Pregnant or lactating women;
- Left ear disease, acute exacerbation of asthma or chronic obstructive pulmonary disease, or other conditions precluding taVNS treatment;
- Presence of cardiac pacemaker, implantable cardioverter-defibrillator (ICD), or other implantable stimulators (e.g., VNS or deep brain stimulators).

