4.3 Withdrawal Criteria

Desire to pursue other treatments or voluntary withdrawal from the trial without specific reason.

5. Study Treatment Groups

- Group A (Active Stimulation Group): Patients receive standard ACS treatment plus active transcutaneous auricular vagus nerve stimulation (taVNS), twice daily for 20 minutes each session.
- Group B (Sham Stimulation Group): Patients receive standard ACS treatment plus sham taVNS treatment, twice daily for 20 minutes each session.

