6.2 Concomitant Treatment and Follow-up Visits

All enrolled patients will receive standard post-PCI medication and strict secondary prevention for coronary artery disease.

Follow-up visits will occur at 4, 8, 12, and 16 weeks post-randomization. Follow-up content includes: HAMA, HAMD, BDI, GAD-7, PCL-C, and SF-36 scale assessments; HRV measurement; echocardiography; venous blood tests; assessment of smoking/alcohol cessation and lifestyle improvement; record of follow-up visits (time, location, results); presence of angina or heart failure-related symptoms; occurrence of MACE (time, management, outcome); adverse reactions.

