6.3 Patient Adherence and Withdrawal

Adherence: A trusting relationship will be established to ultimately improve subject adherence.

Withdrawal: Subjects found during follow-up to have poor treatment adherence, including self-discontinuation of device use, heavy smoking, and severely poor lifestyle/dietary habits; development of other serious new illnesses post-procedure that may affect study endpoints; loss to follow-up.

7. Evaluations

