7.2.3 Physical Examination and Vital Signs

Consciousness, neurological reflexes, breath sounds, heart sounds, skin and mucous membrane condition.

8. Adverse Event Reporting

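### Suicide risk and depression severity limit entry, but neither is named in the safety evaluation or the withdrawal rules, and detection rests on general adverse event reporting

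*Protocol*

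**What the plan says.** **Entry.** Protocol 4.1 requires a DSM-V diagnosis of major depressive disorder in a patient who "refuses psychiatric consultation and declines antidepressant medication or psychotherapy". It sets a severity window of "HAMD-17 score ≥ 7 and < 24". Section 4.2 lists "High suicide risk" as an exclusion, without an instrument or cut-off. The grading in 2.2.1 reads "Severe depression: Total score > 24".

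**Treatment and follow-up.** Active or sham stimulation is self-administered at home for 8 weeks, with a daily diary card that is checked at visits (6.1). Visits are at Weeks 4, 8, 12 and 16 and include "HAMA, HAMD, BDI, GAD-7, PCL-C, and SF-36 scale assessments", together with adverse reactions and MACE (6.2).

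**Safety evaluation.** Section 7.2 has three parts: vital signs with cardiorespiratory symptoms (7.2.1), laboratory tests and echocardiography (7.2.2), and an examination covering "Consciousness, neurological reflexes, breath sounds, heart sounds, skin and mucous membrane condition" (7.2.3).

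**Withdrawal.** Section 4.3 gives "Desire to pursue other treatments or voluntary withdrawal from the trial without specific reason". Section 6.3 adds poor adherence and "development of other serious new illnesses post-procedure that may affect study endpoints; loss to follow-up".

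**Event reporting and oversight.** Section 8.1 defines adverse and serious adverse events in general terms. Section 8.2 requires events arising in the treatment period to be recorded in detail, and serious events to be reported within 24 hours. Section 9.6 plans no Data Monitoring Committee, on the ground that adverse reactions are few and mild.

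**The concern.** Deterioration of depression, including new suicidality, is the most foreseeable psychiatric harm in this population. All participants have the disease, all have turned down consultation and have declined medication or psychotherapy, and half are assigned to sham. The protocol recognises both risks by using them to restrict entry. Once a patient is enrolled, its dedicated safety and withdrawal sections no longer mention the disease under study.

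A site that followed 7.2, 4.3 and 6.3 to the letter would have no instruction to treat a rising HAMD or BDI, or a suicidal response, as safety information. Two things are at stake: prompt recognition of a patient in difficulty, and a planned account of how many patients deteriorated in each arm. The waiver of a monitoring committee in 9.6 does not fill the gap, because its reasoning concerns adverse reactions and does not discuss worsening of the depression.

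**Working it through.** The plan states no figure on this point to reproduce. The check sets the sections side by side.

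**1. Follow the two entry limits forward.**

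| Section | Suicide risk | Depression severity |
|---|---|---|
| 4.1, 4.2 (entry) | exclusion | HAMD-17 below 24 |
| 7.2.1 to 7.2.3 (safety) | not named | not named |
| 4.3, 6.3 (withdrawal) | not named | not named |
| 6.2 (visits) | not named | HAMD and BDI collected, no result tied to a step |
| 7.1 and 2.2 (efficacy) | not named | HAMD and BDI are endpoints |
| 8.1, 8.2 (events) | general wording only | general wording only |

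Suicide is mentioned once in the protocol, in 4.2.

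**2. Could the withdrawal wording cover a worsening patient?** Section 4.3 depends on the patient's own wish. Section 6.3 speaks of "development of other serious new illnesses post-procedure that may affect study endpoints; loss to follow-up". Worsening of the depression that qualified the patient for the trial is not clearly an additional or a new illness. What remains is self-referral, in a group selected for having refused consultation.

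**3. Could Section 8 cover it?** In part. The adverse event definition in 8.1 takes in signs, symptoms and disease whatever the cause. The serious category includes death, life-threatening events, hospitalisation and other medically important events. A suicide attempt, a psychiatric admission or worsening that someone reports would qualify. Nothing makes a change on HAMD or BDI by itself an event to be recorded.

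**4. How much of the follow-up does routine recording span?** Treatment lasts 8 weeks (6.1) and follow-up 16 weeks (6.2).

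- Follow-up after treatment ends: 16 − 8 = 8 weeks, and 8/16 = 50%.
- Visits after treatment ends: Weeks 12 and 16, which is 2 of 4.

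In that second half, 6.2 still collects adverse reactions and MACE. The serious-event sentence in 8.2 states no period of its own. The limit therefore falls on the detailed recording of adverse events, and a site may read it differently.

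**5. How much usable information is already scheduled?** With 120 patients (9.1):

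- All visits: 120 × 4 = 480 HAMD and 480 BDI assessments.
- After treatment ends: 120 × 2 = 240 of each.
- If the planned 10% loss all occurred before Week 4 (assumption): 120 × 0.90 = 108 patients, so 108 × 4 = 432 and 108 × 2 = 216 of each.

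The range is 432 to 480 assessments per scale, none designated as safety data. The protocol gives no basis for estimating how many would show deterioration, so no such count is offered.

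**6. Is the severity boundary settled?** No. Entry stops below 24, while 2.2.1 has "Severe depression: Total score > 24", so a score of exactly 24 is outside entry yet graded moderate. The introduction describes moderate or severe depression as the target, and 6.1 describes mild to moderate. Any safety use of HAMD needs these statements reconciled first.

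**The case against.** The strongest reply is that Section 8 already provides a route. Its definitions are broad and causality is not required, serious events go forward within 24 hours, and adverse reactions are asked about at every visit and on a daily diary. This stands, and it rules out one tempting inference: that a patient who worsens is counted only as efficacy data. The documents do not support that. What is missing is targeted, systematic capture.

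Four other inferences also go too far.

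- **No contact before Week 4.** Section 6.1 provides a diary, telephone help and site visits. Diary checks are tied to assessment visits, but earlier contact is possible.
- **The trial could not compare deterioration between arms.** Scores are recorded per patient, and counts by arm could be derived afterwards. The protocol simply does not plan them as a safety outcome.
- **Severe depression is a listed exclusion.** It is kept out by the upper HAMD limit among the inclusion criteria.
- **Patients are held without antidepressants for 16 weeks.** They are advised to accept treatment before enrolling (6.1), may leave to seek it (4.3), and half are assigned active stimulation. No passage expressly bars antidepressants after entry; 9.2.2 mentions interfering treatment only as a possible per-protocol violation.

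It can also be said that entry criteria need not be repeated as withdrawal criteria, that further tabulations may sit in an analysis plan, and that the consent pages are not available to judge. All three are fair. However, the choice of safety assessments and withdrawal rules belongs in a protocol, and this protocol has dedicated sections for both that omit the disease being treated.

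**Conclusion.** The point holds as a gap in the designated safety data. It does not show that deterioration would go unrecorded. Two risks serious enough to restrict entry are absent from 7.2, 4.3 and 6.3, and the general reporting in 8.2 ties detailed adverse event recording to a treatment period that is half of follow-up. Between 432 and 480 scheduled assessments on each scale could serve as safety information and are not assigned that use.

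This rests on reading the treatment period as the 8 weeks of stimulation, and on the sections available. A reader might go further and infer a specific number of missed cases, or that the entry limits should act as stopping or referral triggers. The documents support neither: they give no deterioration rate, and what should follow when a limit is passed is a clinical decision for the sponsor.

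**What to change.** By protocol amendment:

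1. Add worsening depression and emergent suicidality to 7.2 as safety outcomes, drawn from the HAMD and BDI already collected at Weeks 4, 8, 12 and 16. This assumes that the versions used contain a suicide item; the protocol does not list the items, so the sponsor should confirm it.
2. State in 8.2 that these outcomes are captured as safety data through Week 16.
3. Report the number of patients affected in each arm. Done at the end of the trial, this needs no interim analysis (9.5).
4. Reconcile 4.1, 4.2, 4.3, 6.3, 7.2 and 8 on how a patient who passes the entry limits after enrolment is handled, including the boundary at a score of 24. The threshold, the reviewer and the clinical response are the sponsor's decision. The psychiatrist's role in 6.1 is stated for screening only.

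The cost is the amendment, a line on the visit form and time for review. No new scale or visit is needed. The downside is that some patients may be directed to care, and their later scores will reflect it.
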